6. DATA ANALYSIS

6.1. Analysis Populations

6.1.1. Patient population

The population for analysis will comprise all patients recruited into the study, meeting eligibility criteria as assessed in the survey screener, and completing all questions in the survey.

The outcomes will be summarised for all eight specified countries combined, and separately for Germany and for the seven countries combined not including Germany for the reasons outlined in Section 3.2.1.

6.1.2. Neurologist population

The population for analysis will comprise all neurologists recruited into the study, meeting eligibility criteria as assessed in the survey screener, and completing the survey.

The outcomes will be summarised for all eight specified countries combined, and separately for Germany and for the seven countries combined not including Germany for the reasons outlined in Section 3.2.1.

The sub-population for analyses will be the neurologists who have ever prescribed TROBALT.

6.2. Analyses

6.2.1. Patient survey analysis

Patient demographics and indication for TROBALT use (epilepsy/ other) will be summarised using descriptive statistics for continuous data and proportions for categorical data.

The primary outcome is the proportion of patients answering each question of patient understanding of the risks associated with TROBALT correctly. Point estimates for the proportion with correct responses, and associated confidence intervals, will be calculated for each question about the risks of TROBALT. In the case of multiple choice questions, the number and proportion of patients reporting each response will also be provided.

The proportion of correct answers to survey questions will be summarised overall, and by demographic subgroups such as country. Consideration of these subgroups may highlight differences in patients' responses. Although the sample size in some subgroups may be relatively small and have low precision, data will be grouped into 2-3 sub-categories as appropriate to identify potential trends in patient understanding including:

- Demographics (gender, age, education level)
- Country
- TROBALT use (e.g., months using TROBALT, method of obtaining TROBALT (pharmacy, neurologist, mail, internet), whether the patient read the PIL)

The survey results will be presented with Germany included in the overall study population, then separately for Germany and the remaining specified European countries.

This study is descriptive; hence there will be no formal statistical testing completed.

6.2.2. Neurologist survey analysis

The primary outcome is the proportion of neurologists answering each question of the understanding of the risks associated with TROBALT correctly. Point estimates for the proportion with correct responses, and associated confidence intervals, will be calculated for each question about the risks of TROBALT. In the case of multiple choice questions, the number and proportion of neurologists reporting each response will also be provided.

The proportion of correct answers to survey questions will be summarised overall, and separately for those neurologists who have prescribed TROBALT. Exploratory analyses may include stratification by country.

The survey results will be presented with Germany included in the overall study population, then separately for Germany and the remaining specified European countries.

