2. OBJECTIVE(S)

The objectives of this study are:

1. To assess patients' understanding of the significant risks associated with TROBALT as evaluated by a survey instrument.
2. To assess prescribers' understanding of the significant risks associated with TROBALT as evaluated by a survey instrument, for those who should have received the letter containing TROBALT Physician's Guide, and specifically for the subset of prescribers who have prescribed TROBALT.

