3.2.2. Neurologists prescribing anti-epileptic drugs

This survey aims to recruit a random sample of 300 neurologists prescribing AEDs and who have been sent the TROBALT Physician's Guide. A sample of 200 neurologists will be recruited from across the following countries (United Kingdom, Sweden, Denmark, Switzerland, Spain, Slovakia and Norway), and up to 100 neurologists will be recruited from Germany. If required, additional EU countries may be included in the survey to reach the minimum recruitment target. The recruitment will be from among those who have prescribed an anti-epileptic drug (AED) at least once in the last 3 months, and who were on the list to which a letter including the Physician's Guide TROBALT was distributed. The survey will aim to recruit at least 75 physicians (from the seven specified countries) and 50 physicians from Germany with experience of prescribing TROBALT for sub-analyses, as these individuals would be expected to be more aware of the risks of TROBALT. The sub-group of neurologists commonly referred to as 'epileptologists' are known from past experience to be the specialists who first initiate prescriptions of a new AED and were therefore specifically targeted for promotional activity by GSK and are the primary target of this survey.

As with the patient population, these numbers reflect a trade-off between what is practical in terms of recruitment, given the relatively low predicted prescribing of TROBALT, and providing sufficient precision around outcome estimates (proportion giving correct responses per question), and also to allow analysis of the sub-sample of neurologists who have prescribed TROBALT.

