The information in this survey and the Patient Information Leaflet (PIL) should not take the place of talking with your health care professional. If you have any questions about your condition or treatment, or if you would like more information about TROBALT, talk to your health care professional. The Patient Information Leaflet can be obtained from the following website: <http://www.gsk.com/products/prescription-medicines/trobalt.htm>.

Thank You

Appendix 5 Questionnaire for Neurologists who Prescribe AEDs and were Sent the TROBALT Letter Containing the Physician's GuideScreening Questions:

1. Do you agree to take part in this survey?
 - **Yes**
 - No (Exclude)

2. When was the last time you prescribed an anti-epileptic drug for a patient?
 - **Less than a month ago**
 - Between 1 and 2 months ago
 - Between 2 and 3 months ago
 - More than 3 months ago (Exclude)

3. Have you ever prescribed TROBALT?
 - **Yes**
 - No
 - I don't know

4. In which country is your primary medical practice?
 - **Germany**
 - Denmark
 - United Kingdom
 - Switzerland
 - Sweden
 - Spain
 - Slovakia
 - Norway
 - Other (exclude)

[QUOTAS WILL BE ESTABLISHED FOR 200 NEUROLOGISTS FROM UK, SWEDEN, DENMARK, SWITZERLAND, SPAIN, SLOVAKIA, AND NORWAY; AT LEAST 75 SHOULD HAVE PRESCRIBED TORBALT. QUOTA OF 100 NEUROLOGISTS FROM GERMANY, OF WHICH AT LEAST 50 SHOULD HAVE PRESCRIBED TROBALT.]

5. Are you an employee of GlaxoSmithKline or [REDACTED] Corporation?
 - **Yes (Exclude)**
 - **No**

Questionnaire for Neurologists who Prescribe AEDs and Were Sent the TROBALT Letter Containing the Physician's Guide

[CORRECT ANSWERS ARE INDICATED IN BOLD]

6. For which of the following conditions is TROBALT approved for use?
- Migraine
 - **Partial-onset seizures**
 - All types of seizures
 - All of the above
 - None of the above
 - I don't know
7. Is TROBALT indicated for use as monotherapy?
- Yes
 - **No**
 - I don't know
8. What is the maximum recommended daily maintenance dose of TROBALT for most patients? (Please select the best response.)
- 600 mg
 - 900 mg
 - **1200 mg**
 - 2000 mg
 - None of the above
 - I don't know
9. Which one of the following statements is true? (Please select the best response.)
- TROBALT should be taken once a day.
 - TROBALT should be taken twice a day.
 - **TROBALT should be taken three times a day.**
 - TROBALT should be taken four times a day.
 - None of the above
 - I don't know

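### Minimum TROBALT-prescriber numbers are laid over a sample called random, so the pooled neurologist figure is likely to overstate knowledge if prescribers are scarce on the mailing list

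*Protocol*

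**What the plan says.** Objective 2 (Protocol Section 2) sets two targets for the neurologist survey: understanding "for those who should have received the letter containing TROBALT Physician's Guide, and specifically for the subset of prescribers who have prescribed TROBALT". The first is the mailing list; the second is a subset of it.

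Section 3.2.2 describes the sample: "This survey aims to recruit a random sample of 300 neurologists prescribing AEDs and who have been sent the TROBALT Physician's Guide". Section 8 likewise says that those invited are a random draw from recipients of the Guide.

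Section 3.2.2 then asks for "at least 75 physicians (from the seven specified countries) and 50 physicians from Germany with experience of prescribing TROBALT", and gives the reason: "as these individuals would be expected to be more aware of the risks of TROBALT". It justifies the sample sizes as a compromise "given the relatively low predicted prescribing of TROBALT". The note under Question 4 in Appendix 5 turns the minimums into quotas ("AT LEAST 75 SHOULD HAVE PRESCRIBED TORBALT", spelling as printed), with at least 50 of 100 in Germany. The Protocol Summary says approximately 50 for Germany.

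For the analysis, Section 6.2.2 states: "The proportion of correct answers to survey questions will be summarised overall, and separately for those neurologists who have prescribed TROBALT". Sections 6.1.2 and 6.2.2 add results for Germany and for the seven other countries. The protocol states no weighting to the list and no result for non-prescribers alone. Section 8 names self-selection and the German restriction as limitations, but not the prescriber quota.

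**The concern.** A sample topped up to a minimum number of prescribers is no longer a plain random sample of the list. If prescribers are scarcer on the list than the minimum requires, they are over-represented in any pooled proportion. The protocol supplies both conditions for an upward shift: prescribing is expected to be low, and prescribers are expected to know more.

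The survey exists to judge whether the educational plan works. An upward shift in the overall proportion flatters that plan, and the confidence interval does not show it: more respondents recruited under the same quota narrow the interval and leave the shift where it is.

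**Working it through.** **1. The plan's own precision figure.** Margin = 1.96 × √(p(1−p)/n). For n=250 and p=0.60: 1.96 × √(0.24/250) = 6.07 points, against ±6.0 in Section 7. At 60% correct the formula gives 6.79 for n=200 (Table 1: 7.0) and 5.54 for n=300 (Table 1: 5.7). Table 1 thus rests on simple random sampling, with no allowance for the quota.

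**2. Prescriber share implied by the floors.** Seven countries: 75/200 = 37.5%. Germany: 50/100 = 50%. All eight: 125/300 = 41.7%.

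**3. When the floor binds.** The probability that a random sample of 200 contains at least 75 prescribers (binomial) is below 0.00001 at a list share of 20%, 1.4% at 30%, 53% at 37.5% and 98.7% at 45%. The floor therefore changes the sample when the list share is below roughly 37.5%, and has little or no effect above it.

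**4. Size of the shift.** Let w be the prescriber share in the sample, π the share on the list, and d the difference in proportion correct between prescribers and non-prescribers. Pooled minus list value = (w − π) × d. The protocol gives neither π nor d, so both are assumed. For the seven countries (w = 0.375), in percentage points:

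| List share π | d = 10 | d = 20 | d = 30 |
|---|---|---|---|
| 5% | 3.25 | 6.5 | 9.75 |
| 10% | 2.75 | 5.5 | 8.25 |
| 20% | 1.75 | 3.5 | 5.25 |
| 30% | 0.75 | 1.5 | 2.25 |
| 37.5% | 0 | 0 | 0 |

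Only two cells exceed Table 1's ±7.0 for n=200 at 60% correct: the 30-point gap at list shares of 5% and 10%.

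**5. Why a shift inside the margin still matters.** Take π = 10%, with 80% of prescribers and 60% of non-prescribers correct.
- Pooled: 0.375 × 80 + 0.625 × 60 = 67.5%, margin 1.96 × √(0.675 × 0.325/200) = ±6.5, standard error 3.31.
- List value: 0.10 × 80 + 0.90 × 60 = 62.0%.
- The shift of 5.5 points is 5.5/3.31 = 1.66 standard errors. The nominal 95% interval then contains the list value with probability about Φ(1.96 − 1.66) = Φ(0.30), roughly 62%.

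**6. Price of weighting in the same example.** Stratified variance = 0.10² × 0.16/75 + 0.90² × 0.24/125 = 0.00158, so the margin is 1.96 × √0.00158 = ±7.8. The effective sample size is 200/(0.10²/0.375 + 0.90²/0.625) = 200/1.323 ≈ 151.

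**7. Eight countries pooled.** Assuming the same π and d everywhere, π = 10% and d = 20 give (0.417 − 0.10) × 20 = +6.3 points. Sections 3.2.1 and 8 limit German recruitment to neurologists who still prescribe TROBALT or still have patients on it. If all 100 German respondents are prescribers, w = 175/300 = 58.3% and the shift is +9.7 points.

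**The case against.** The strongest reply has five parts.

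*The quota is only a floor.* This stands. A reader might infer that the plan fixes the prescriber share. It does not: the seven-country wording is a minimum, and the German sample is up to 100 with about 50 prescribers. If prescribers already make up about 37.5% of the list, the seven-country floor does essentially nothing.

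*Weighting may be in a statistical analysis plan.* One may exist, but it is not at hand, and Section 6.2.2 neither prescribes nor excludes weights. Silence on weights alone would be no finding. What remains is inside the protocol: it calls the sample random, sets quotas that can change its make-up, names a pooled summary, and omits the quota from its limitations.

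*Prescribers and Germany are already shown separately.* This reduces the harm. Non-prescriber results follow by subtraction if counts are given. To re-weight, however, a reader also needs the list share, which the protocol does not plan to report.

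*Epileptologists are called the primary target, and the enrichment is for sub-analyses.* True of Sections 1 and 3.2.2. But Objective 2 names all letter recipients and gives TROBALT prescribers their own estimate. Having ever prescribed TROBALT is also a different question (Appendix 5, Question 3) from being an epileptologist (Question 24).

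*Representativeness is already disclaimed.* Section 8 does say that respondents are self-selected. That is a different mechanism, and its direction is not stated. Here the protocol's own expectations give the direction.

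**Conclusion.** The point holds conditionally. If prescribers are less than about 37.5% of the seven-country list, the pooled overall proportion is likely to be too high as a statement about all neurologists sent the Guide. Under assumed list shares of 5% to 30% and gaps of 10 to 30 points, the seven-country shift is about +1 to +10 points, and mostly within the ±7.0 margin. It is zero where the floor does not bind.

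A reader might infer that overstatement is established, or that it has one definite size above the margin. The documents do not support either. They give a direction (low prescribing, more aware prescribers) but no list share and no knowledge gap. The larger values depend on a 30-point gap for which the protocol offers no basis. Seven-country shifts should be compared with the n=200 margin, not the n=300 one.

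The eight-country shift is less certain still, because the German recruitment rules do not agree with each other.

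**What to change.** - **Main presentation (Section 6.2.2).** Report ever-prescribers and non-prescribers side by side, and say where an answer of not knowing to Question 3 is counted.
- **Seven-country overall figure.** Add an estimate weighted by prescriber status, with a stratified confidence interval. Take the prescriber share from Question 3 among everyone who reaches it, including those turned away once a quota is full. This is valid only if invitations stay a random draw from the list, as Section 3.1 says, and are not redirected towards known prescribers. Use two strata, and add country only where cells allow: 75 prescribers over seven countries average about 11 per country (75/7).
- **If weighting is not adopted.** Label the overall figure as describing a prescriber-enriched quota sample.
- **Germany.** Do not weight to the German list until Sections 3.2.1 and 8 (continuing prescribers only) are reconciled with the Protocol Summary and Appendix 5 (about half need ever have prescribed). If only continuing prescribers are recruited, no weight can represent German non-prescribers.
- **Floor.** Reconcile the screening note in Section 4.2 (at least 100 prescribers) with 75 + 50 = 125 in Section 3.2.2.
- **Section 8.** Name the prescriber quota as a limitation.

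The cost is logging the screen-outs, some added text, and a moderately wider interval for the weighted figure: ±6.5 becomes ±7.8 in the example above. Weights based on the screener do not remove self-selection, and the text should say so.

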7. PRECISION BY SAMPLE SIZE

Table 1 summarises the margin of error at the 95% confidence level provided by varying sample sizes and estimates of percentage of patients indicating a correct response. For example, if the estimate of the percentage of patients indicating a correct response to an individual survey question is 60%, then a sample of 250 patients will provide a margin of error of ± 6.0 percentage points of this estimate with a 95% confidence interval. Subgroups of the total sample will have smaller numbers of patients, resulting in larger margins of error and therefore provide estimates with lower precision.

Table 1 Sample size and precision estimates

Sample Size	Proportion of Correct Responses to Each Question						
	50	60	70	75	80	85	90
	Precision/ Margin of Error ($\pm\%$) with 95% Confidence Interval						
50	14	14	12	11	10	9.0	8.0
100	10	10	9.0	8.0	8.0	7.0	6.0
150	8.0	8.0	7.3	7.0	6.7	5.7	4.7
200	7.0	7.0	6.5	6.0	5.5	5.0	4.0
250	6.0	6.0	5.6	5.4	4.8	4.6	3.6
300	5.7	5.7	5.3	5.0	4.7	4.0	3.3
350	5.1	5.1	4.9	4.4	4.3	3.9	3.1
400	5.0	4.8	4.5	4.3	4.0	3.5	3.0
450	4.7	4.4	4.2	3.9	3.8	3.2	2.7
500	4.4	4.2	4.0	3.8	3.6	3.2	2.6

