3. INVESTIGATION PLAN

3.1. Study Design

This study is sponsored by GlaxoSmithKline (GSK), and will be conducted by [REDACTED] an international research consultancy.

This is a cross-sectional study of physicians' and patients' understanding of the significant risks associated with TROBALT.

Physicians will be recruited by selecting a random sample of neurologists from lists provided by GSK in each country. The list includes names of all potential TROBALT prescribers who were mailed an introductory letter including the Physician's Guide for TROBALT (Appendix 1). Following recruitment, neurologists' understanding of the potential risks associated with TROBALT will be evaluated using an online survey. Each invitation will include information on how to access the survey on-line, and will include a unique code to ensure that the invitation is used only once.

The primary method of recruiting patients is through their physicians. In countries in which a list of current TROBALT prescribers can be obtained, a random sample of prescribers in each country will be selected. Otherwise, the sample will come from the list of neurologists who were mailed the Physician's Guide, who have not participated in the neurologist survey. Sampled prescribers will be asked to provide survey invitations to their patients being treated with TROBALT. Each prescriber will be given 10 invitations and asked to provide these invitations to up to 10 consecutive patients who have been prescribed TROBALT in the last 3 months. If the patient response rate using this recruitment method is lower than expected, then other options will be identified including patient panels where available.

Following recruitment, patients' understanding of the potential risks associated with TROBALT will be evaluated using an online survey or the same survey instrument delivered during a telephone interview. The latter option aims to accommodate individuals who are not comfortable with online technology or are not computer literate. Each invitation will include information on how to access the online survey and will also provide the toll-free number for accessing the Survey Call Centre.

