3.2. Study Populations

3.2.1. Patients using TROBALT

This survey aims to recruit 350 patients who are currently being treated with TROBALT or who have received TROBALT within the last 3 months. These numbers reflect a trade-off between what is practical in terms of recruitment, given the relatively low predicted uptake of TROBALT, and providing sufficient precision around outcome estimates (proportion giving correct responses per question) (Section 8).

The selected countries were the first five countries to launch TROBALT (Germany, Denmark, United Kingdom, Switzerland and Sweden) and an additional three countries with launch in 2011, but with relatively high rates of uptake of TROBALT (Spain, Slovakia and Norway). The selection of countries includes Switzerland, which is not part of the European Union. However, the key messages regarding the risks with TROBALT are in alignment. The rationale for surveying the first five countries to launch is so that any issues identified from these countries regarding the effectiveness of the Physician's

Guide and PIL in communicating the risks of TROBALT can be addressed as soon as possible, and the key messages can be revised in a timely manner. In addition, these countries are likely to provide the greatest number of neurologists with experience of prescribing TROBALT, and their patients.

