Two-hundred fifty patients will be recruited from across the following countries (United Kingdom, Sweden, Denmark, Switzerland, Spain, Slovakia and Norway). If required, additional EU countries may be included in the survey to reach the minimum recruitment target. Up to one hundred patients will be recruited from Germany, which was one of the earliest countries to launch and currently has the highest volume of use of TROBALT in Europe. However, it should be noted that on May 31, 2012, following the reimbursement process in Germany, GSK chose not to enter into price negotiations and TROBALT will not be available for new patients from July 2012 until further notice. Patients currently on TROBALT prior to May 31, 2012 will continue to be able to fill their TROBALT prescriptions in Germany. Therefore, by November 2012 at the start of the survey, the characteristics of the patients using TROBALT in Germany may differ from the other European countries where new patients will continue to receive TROBALT prescriptions. Additionally, the neurologists included from Germany will only be those who continue to prescribe TROBALT, and this may be a selected population. For these reasons, the survey data from Germany will be analysed with the total study population, as well as separately.

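### Patients are recruited in clusters through their prescribers, but the Section 7 precision figures assume independent patients, so ±6.0 points for 250 patients is a best case

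*Protocol*

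**What the plan says.** Protocol Section 3.1 (Study Design) makes physicians the main route to patients. Prescribers are sampled at random within each country, and "Each prescriber will be given 10 invitations and asked to provide these invitations to up to 10 consecutive patients". Section 8 (Study Limitations) adds that this sample is proportionate and stratified by country. Patient panels are mentioned only as a fallback if response is low.

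Section 3.2.1 sets the targets. "This survey aims to recruit 350 patients who are currently being treated with TROBALT", of whom 250 come from the seven countries other than Germany and up to 100 from Germany. It justifies these numbers partly by the precision they give for each question.

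Section 7 (Precision by Sample Size) gives that precision. "Table 1 summarises the margin of error at the 95% confidence level provided by varying sample sizes" and by the percentage answering correctly. Its worked example is that, at 60% correct, "a sample of 250 patients will provide a margin of error of ± 6.0 percentage points". The only caveat there is that subgroups are smaller and so less precise. Section 8 discusses representativeness and self-selection but not similarity among patients of one prescriber.

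For the analysis, Section 6.2.1 says: "Point estimates for the proportion with correct responses, and associated confidence intervals, will be calculated for each question". It names no interval method.

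**The concern.** The prescriber is the first sampling unit, and each prescriber may contribute several patients. The protocol itself gives reason to expect those patients to resemble one another in what they know. The launch letter (Appendix 1) asks prescribers to discuss the risks with patients before starting treatment, and question 15 of the patient questionnaire (Appendix 3) lists the neurologist as a source of knowledge about side effects. Positive correlation within prescribers means that 250 patients carry less information than 250 independent ones.

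The study is descriptive and plans no tests, so a proportion with its confidence interval for each question is the whole primary result. If clustering is ignored in planning, the precision offered in support of 250 and 350 patients is too optimistic. If it is also ignored in the analysis, the intervals will be too narrow.

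There is a practical side as well. Intervals that allow for clustering need to know which prescriber recruited each respondent. Section 3.3.1 provides a unique code per invitation but does not say that it identifies the prescriber. If that link is not built before invitations go out, a later analysis plan may be unable to recover it.

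**Working it through.** **Inputs from the protocol.** Confidence level 95%, n = 250, 60% correct, stated margin ±6.0 points (Section 7); at most 10 invitations per prescriber (Section 3.1).

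**Inputs not in the protocol, so assumed.** Completed surveys per prescriber, m = 2, 5 or 10 (10 being the ceiling); ICC = 0.01, 0.05 or 0.10.

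**Step 1: reproduce the stated figure.** For independent patients, margin = 1.96 × √(p(1−p)/n) = 1.96 × √(0.60 × 0.40 / 250) = 6.07 points. The distance from 60% to either the 2.5% or the 97.5% quantile of a binomial distribution with n = 250 is exactly 6.0. Both calculations treat patients as independent, that is, they use a design effect of 1.

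**Step 2: allow for clustering.** With equal clusters, design effect DE = 1 + (m − 1) × ICC. The margin becomes 6.07 × √DE, and the effective sample size is 250 / DE.

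| m | ICC | DE | Margin (± points) | Effective n |
|---|---|---|---|---|
| 2 | 0.01 | 1.01 | 6.10 | 248 |
| 2 | 0.05 | 1.05 | 6.22 | 238 |
| 2 | 0.10 | 1.10 | 6.37 | 227 |
| 5 | 0.01 | 1.04 | 6.19 | 240 |
| 5 | 0.05 | 1.20 | 6.65 | 208 |
| 5 | 0.10 | 1.40 | 7.19 | 179 |
| 10 | 0.01 | 1.09 | 6.34 | 229 |
| 10 | 0.05 | 1.45 | 7.31 | 172 |
| 10 | 0.10 | 1.90 | 8.37 | 132 |

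**Step 3: when does it start to matter?** Setting the margin to 7 points and solving for the ICC gives 0.037 with m = 10, 0.082 with m = 5, and 0.33 with m = 2. Small clusters are almost harmless, while large ones matter even at a modest ICC.

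**Step 4: effect on an unadjusted interval.** If an interval ignored the clustering, its coverage would be 2Φ(1.96/√DE) − 1: about 93% at DE 1.2, 90% at 1.45 and 85% at 1.9.

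**Step 5: the full patient sample.** At n = 350 and 60% correct, the independent margin is 1.96 × √(0.24/350) = 5.13 (Table 1 prints 5.1). It becomes ±5.16 at m = 2, ICC 0.01 and ±7.07 at m = 10, ICC 0.10.

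**The case against.** The strongest reply is that the loss may be negligible. Ten is a ceiling on invitations, not an expected number of completed surveys. Section 3.2.1 expects relatively low uptake, and where no list of TROBALT prescribers exists the sample comes from the general mailing list, so many prescribers may contribute only one or two patients. With 2 completers and an ICC up to 0.10, or with an ICC of 0.01 at any cluster size up to 10, the margin grows by about 0.3 points or less. Patients from panels would not come through this step at all. Sample size was also openly a compromise with feasibility, and no decision rule depends on ±6.0. All of this stands. It limits the size of the point, but it does not make Section 7's unqualified figure right.

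A reader might infer that the planned confidence intervals themselves assume independence. The protocol does not say so: Section 6.2.1 names no method, and a statistical analysis plan, which is not shown, may specify a cluster-adjusted one. What can be faulted is the planning statement in Section 7.

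A reader might also take the n = 50 row of Table 1 for an arithmetic error. It prints 12, 11, 10 and 9.0 for 70, 75, 80 and 85% correct, where the normal formula gives 12.7, 12.0, 11.1 and 9.9. But Section 7 names no formula. The normal formula matches only 20 of the 70 cells to one decimal, whereas every cell matches, after rounding, the distance from the percentage to one of the 2.5% and 97.5% binomial quantiles. At n = 50 the printed values are the upper-side distances (the lower side gives 14, 13, 12 and 11). Quoting the shorter side is open to criticism, but replacing one row with normal-formula values would mix two methods, and the matter is separate from clustering.

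Finally, tagging a response with its prescriber may link a patient to a small practice, while Sections 5 and 9.2 promise separated identifiers and confidentiality. That is a fair constraint on how the fix is made.

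**Conclusion.** The point holds for the patient survey. Recruitment is mainly clustered by prescriber, and Section 7's ±6.0 points for 250 patients at 60% correct is obtained only with a design effect of 1, so it is a best case. Over the assumed ICC range of 0.01 to 0.10 and 2 to 10 completers per prescriber, the margin runs from about ±6.1 to ±8.4. Where in that range the survey would fall cannot be settled from the protocol, so it would be too strong to say that the stated precision will not be reached to any material degree. The range rests on equal cluster sizes. Unequal clusters would widen the margins, and country stratification could narrow them slightly. The neurologist survey is not affected, because neurologists are sampled individually.

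**What to change.** 1. **Section 7:** state that Table 1 assumes independent patients, and show the patient margin over a stated range of design effects that includes small ones. For n = 250 at 60% correct, design effects of 1.0 to 1.9 give ±6.1 to ±8.4 points. Label the range as an assumption.
2. **Section 3.3.1:** have the existing unique invitation code carry a pseudonymous identifier of the recruiting prescriber. The survey contractor should hold the key, and it should not go to the sponsor, in keeping with Sections 5 and 9.2. This must be in place before invitations are sent.
3. **Section 6.2.1:** compute patient confidence intervals with prescriber as cluster and country as stratum, for example by survey linearisation or a robust (GEE) variance.

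The cost is one or two sentences in each of these sections and a coding convention. Reported patient intervals would be somewhat wider, and the prescriber link needs care where a practice has few TROBALT patients. No extra patients are needed.
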